The first published systematic review, which has recently been updated, showed that EC with nicotine help smokers quit for at least 6 months compared with no nicotine e-cigarettes (RR= 2.29, 95% CI: 1.05-4.96; 9% vs. 4%) [5]. The review gives these findings a 'low' confidence rating using GRADE standards, not because of poor quality studies, but because the systematic review included only two studies.

There is good rationale for why EC could help people stop in that they can deliver nicotine and alleviate urges to smoke. However, more, well-designed, clinical trials are needed to confirm this.

Changes from planned analysis in the protocol

None.

Changes from SAP version 1.0

Not applicable.

Study objectives and endpoints

Study objectives

Primary Objective

To determine the 12-month sustained, biochemically validated abstinence rates in smokers using EC compared to smokers using standard NRT.

Secondary Objectives

1. Abstinence rates between 6 and 12 months.
2. Abstinence rates at 4 weeks and 6 months.
3. Effects of the two treatments on smoking reduction in participants who did not achieve full abstinence.
4. Changes in urges to smoke and other tobacco withdrawal symptoms at 1 and 4 weeks.
5. Ratings of the two treatment approaches by patients.
6. Rates of adverse reactions associated with the use of EC compared to standard NRT.
7. Cost-effectiveness of EC compared to standard NRT.

Outcome measures

Primary outcome measure

The primary outcome measure is carbon monoxide (CO) validated sustained abstinence rates at 52 weeks post target quit date (TQD), defined as per Russell Standard [6].

Secondary outcome measures

The secondary outcome measures are:

1. CO validated sustained abstinence rates between 24 and 52 weeks
2. Sustained abstinence rates at 4 and 24 weeks post TQD (CO validated at 4 weeks)
3. 7-day point prevalence abstinence at 4, 24 and 52 weeks
4. Smoking reduction in participants who did not achieve full abstinence
5. Changes in urges to smoke and other tobacco withdrawal symptoms at 1 and 4 weeks
6. Treatment ratings (e.g. satisfaction, helpfulness)
7. Adverse reactions
8. Cost-efficacy of the interventions.

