For the primary analysis the proportion of people remaining abstinent at a year will be compared between the study arms using Chi-squared test. The treatment effect will be the risk ratio of abstinence rates for EC relative to NRT. A secondary binomial regression with log link will also be employed, which will allow for a comparison of the two study arms after adjusting for baseline variables identified as significant using a stepwise selection procedure. The analysis will be stratified by the randomization stratification factor, site; this will be done by adjusting the model using a dummy variable for site.

Sensitivity analyses for primary outcome:

A sensitivity analysis will be conducted with only participants who attended at least one treatment session, i.e. who engaged in treatment, included.

Forty two participants received a different EC device due to discontinuation of the original supply. A sensitivity analysis will be conducted with only these participants included.

To deal with participants who switched study products or used the unassigned study product for at least five consecutive days we will include them in the primary analysis in the groups to which they were randomized, but will also conduct a sensitivity analysis where they will be excluded.

Analysis of secondary outcomes

Smoking cessation and reduction outcomes

For the secondary analyses, we will examine the differences between study arms in the proportions of participants with sustained abstinence from 6 to 12 months, and at 4, 24 and 52 week follow-up,

and sustaining a 50% or greater reduction in baseline cigarette consumption and CO levels at 52 weeks, using Chi-squared test/binomial regression.

Sensitivity analyses for secondary outcomes:

Forty two participants received a different EC device due to discontinuation of the original supply. A sensitivity analysis will be conducted with only these participants included.

We will also examine time to relapse in a secondary analysis using a Cox analysis.

Definitions of smoking cessation and reduction outcomes

Primary outcome:

52 week sustained abstinence will be calculated in accordance with the Russell Standard as a self-report of smoking no more than 5 cigarettes since 2 weeks post TQD, validated by a CO reading of <8ppm at the 52 week follow up.

The following rules will apply to the primary outcome:

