| 7. Smoking reduction in participants who did not achieve abstinence at 52-weeks | Self-reported daily cigarette consumption at 52 weeks post TQD reduced by at least 50% of baseline consumption accompanied by a CO reading at 52 weeks reduced by at least 50% compared to baseline. |

NB. Where participants have CO<10 at baseline and report 50% or more cigarette per day reduction at 52 weeks, sensitivity analyses will be carried out including and excluding them.

A sub-analysis of self-reported daily cigarette consumption at 52 weeks reduced by at least 50% of baseline consumption without accompanied CO readings will also be conducted.

Participants with missing data or who report being 'currently quit' at 52 weeks with no further data provided will be classified as non-reducers.

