Where a participant reports being 'currently quit' at 24 weeks post TQD, but has not been contactable to provide any other information, they will be counted as having smoked no more than 5 cigarettes since their last visit, and included as a 24 week sustained abstainer.

4. 7-day point prevalence
at 4-weeks post TQD

Definition: Not a single puff in the last 7-days

Data source: Q+4 CRF

If you have smoked since your last visit/contact, did you smoke at all in the last 7 days?

1. Yes
2. No

5. 7-day point prevalence
at 24-weeks post TQD

Definition: Not a single puff in the last 7-days

Data source: Q+24 CRF

If you have smoked since your last visit/contact, did you smoke at all in the last 7 days?

1. Yes
2. No

6. 7-day point prevalence
at 52-weeks post TQD

Definition: Not a single puff in the last 7-days

Data source: Q+52 CRF

Have you smoked at all in the last 7 days?

1. Yes
2. No

7. Smoking reduction in participants who did not achieve abstinence at 52 weeks

Definition: Daily cigarette consumption of at least 50% of baseline consumption accompanied by a CO reading of 50% of baseline

Data source: Q+52 Post Quit CRF

3b. How many cigarettes per day are you smoking now?

3c. Percentage reduction in number of cigarettes smoked from start of study

Q+52 Validation Visit CRF

3. Record carbon monoxide in expired breath (ppm)

NB. Where participants have CO<10 at baseline and report 50% or more cigarette per day reduction at 52 weeks post TQD, sensitivity analyses will be carried out including and excluding them.

A sub-analysis of self-reported daily cigarette consumption at 52 week follow up reduced by at least 50% of baseline consumption without accompanied CO readings will also be conducted.

Data source: Q+52 Post Quit CRF

3b. How many cigarettes per day are you smoking now?

3c. Percentage reduction in number of cigarettes smoked from start of study

8. Changes in urges to smoke and other tobacco withdrawal symptoms at 1 and 4 weeks.

Definition: Differences in the ratings of urge frequency at 1 and 4 weeks post quit on following scale: not at all, a little of the time, some of the time, a lot of time, almost all of the time, all of the time.

Differences in the ratings of urge strength at 1 and 4 weeks post quit on following scale: no urges, slight, moderate, strong, very strong, extremely strong.

Data source: Q+1 and Q+4 Post Quit CRF

Q6. How much of the time have you felt the urge to smoke over the past week?

1. Not at all

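### Smoking reduction: Appendix 3 words the definition the wrong way round, and testing it among non-abstainers is not a randomised comparison

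*SAP*

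**What the plan says.** **Definition.** Item 7 of the secondary outcomes, under Definitions of smoking cessation and reduction outcomes, sets two conditions: "Self-reported daily cigarette consumption at 52 weeks post TQD reduced by at least 50% of baseline consumption", and this "accompanied by a CO reading at 52 weeks reduced by at least 50% compared to baseline". The analysis text under Smoking cessation and reduction outcomes agrees in direction: "sustaining a 50% or greater reduction in baseline cigarette consumption and CO levels at 52 weeks". Appendix 3, item 7, gives under its Definition label: "Daily cigarette consumption of at least 50% of baseline consumption accompanied by a CO reading of 50% of baseline". Further down the same item, the sub-analysis without CO again has the main-body direction: "A sub-analysis of self-reported daily cigarette consumption at 52 week follow up reduced by at least 50% of baseline consumption".

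**Population.** Secondary objective 3 concerns "smoking reduction in participants who did not achieve full abstinence". The list of secondary outcome measures, item 7 of the definitions and the Appendix 3 item ("Smoking reduction in participants who did not achieve abstinence at 52 weeks") all carry the same restriction. The analysis section plans to compare proportions of participants between arms, the last of them being those "and sustaining a 50% or greater reduction in baseline cigarette consumption and CO levels at 52 weeks, using Chi-squared test/binomial regression". It does not restate the denominator.

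**Related rules.** General analysis principles puts the main analysis of every outcome under intention to treat. Participants lost to follow-up count as non-abstainers, and those with missing reduction data count as non-reducers. Table 5 has no row for reduction.

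**The concern.** There are two separate problems.

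The first is textual. Two places in the plan define the same outcome in incompatible ways, and one of them, taken at its word, describes people who have not cut down. A programmer working from Appendix 3, where the CRF fields are listed, could derive the wrong variable.

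The second is one of design. Whether a participant is a non-abstainer at 52 weeks is settled after randomisation and is close to being the primary outcome itself. If EC raises abstinence, the EC non-abstainers are a differently selected group from the NRT non-abstainers. A difference in reduction rates between them may then reflect who left the group and not any effect on those who stayed. Secondary objective 3 is phrased as an effect of the treatments, and the plan carries no caution that would stop a reader from taking the test as evidence of one.

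**Working it through.** **Definition, worked on one smoker.** Take a baseline of 20 cigarettes a day; half is 10.

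- Main body: the cigarette condition is met at 10 a day or fewer.
- Appendix 3, read literally: it is met at 10 a day or more. Someone still smoking 20 (no reduction) meets it; someone smoking 5 (a 75% reduction) does not.
- The two rules agree only at exactly 10.

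The Appendix 3 CO clause names a level with no direction. Read literally, it is met only at exactly half of baseline, so the number misclassified would depend on how that clause was programmed.

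**The plan's own figure.** The only rates in the SAP that bear on the selection question are the revised abstinence rates under Sample size determination: 10% on usual care (NRT), 17% on EC, 443 per arm, stated power 86%. To reproduce it: the mean rate is 0.135; null SE = √(2 × 0.135 × 0.865 / 443) = 0.02296; alternative SE = √((0.10 × 0.90 + 0.17 × 0.83) / 443) = 0.02284. Power = Φ((0.07 − 1.96 × 0.02296) / 0.02284) = Φ(1.094) = 0.863. The figure reproduces.

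**Selection among non-abstainers.** Assumptions, none of them in the SAP: 15% of randomised NRT participants are reducers; EC does nothing except move an extra 7 points into abstinence; a fraction f of those movers would otherwise have been reducers.

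- NRT rate among non-abstainers = 0.15 / 0.90 = 16.7%.
- EC rate among non-abstainers = (0.15 − 0.07f) / 0.83.
- f = 0: 0.150 / 0.83 = 18.1%, RR 1.08.
- f = 0.5: 0.115 / 0.83 = 13.9%, RR 0.83.
- f = 1: 0.080 / 0.83 = 9.6%, RR 0.58.

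The RR drops below 1 once f exceeds the NRT rate among non-abstainers, here 16.7% (about one mover in six).

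**Range over the assumed share.** In whole participants there are 44 v 75 abstainers, hence 399 v 368 non-abstainers and 31 movers. Rounding to whole people shifts the 15% row slightly from the figures above. P values are from an uncorrected chi-squared test.

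| NRT reducer share | RR, f = 0 | RR, f = 0.5 | RR, f = 1 | p, f = 1 |
|---|---|---|---|---|
| 10% | 1.08 | 0.69 | 0.32 | 0.0001 |
| 15% | 1.08 | 0.82 | 0.57 | 0.004 |
| 20% | 1.08 | 0.89 | 0.71 | 0.021 |
| 25% | 1.08 | 0.93 | 0.78 | 0.052 |
| 30% | 1.08 | 0.95 | 0.83 | 0.092 |

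No result in the f = 0 or f = 0.5 columns reaches p < 0.05.

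**Alternative denominators, 15% share.**

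- All randomised, abstainers counted as not reduced: RR 1.00, 0.76 and 0.53 for f = 0, 0.5 and 1. Changing the denominator alone does not remove the problem.
- All randomised, abstinent or reduced: 141 v 110 (RR 1.28), 125 v 110 (1.14) and 110 v 110 (1.00). This never falls below 1 when nobody has done worse.

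**The case against.** **On the definition.** Appendix 3 is a list of data sources, and the main text refers to it only for how data were collected; the governing definitions are in the body and are clear. Within the same appendix item, the title, the percentage-reduction CRF field, the note on low baseline CO and the sub-analysis all point the right way. This looks like two dropped words. That stands, and it makes a coding error unlikely. It does not make the sentence right. A reader might infer that following Appendix 3 would count people smoking as heavily as before as reducers. The document does not support that: they would also have to meet the CO clause, and someone whose CO is near baseline does not meet it as written.

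**On the denominator.** A reader might see a conflict between the analysis section and the outcome definitions. There is none: the analysis section leaves the denominator unstated, while the definitions consistently name non-abstainers.

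**On the bias.** A reader might infer that the planned comparison must work against EC or will show it as harmful. That goes too far. The direction depends on who the extra quitters would otherwise have been, and the SAP gives no reducer rate. With f = 0 the bias slightly favours EC. A result against EC at p < 0.05 appears only where all movers are would-be reducers and the reducer share is about 20% or less. Even then it would mean a lower reduction rate on one secondary outcome.

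**On the remedy.** An abstinent-or-reduced outcome answers a different question from secondary objective 3 and brings the primary outcome into it. At f = 1 it shows 25% v 25% and hides a 7-point gain in abstinence. This is a fair point. It is a reason to keep the non-abstainer figure and to show the categories separately, not a reason to leave the selected comparison as the only one.

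**Conclusion.** Both parts hold, within limits. The Appendix 3 sentence contradicts the main-body definition, the analysis section and the rest of its own item: reversed for cigarettes, undirected for CO. It is probably a slip, but it stands as a definition and is wrong as written.

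The between-arm test among non-abstainers does not preserve randomisation, despite the intention-to-treat principle set for every outcome. Its bias can go either way: RR 1.08, 0.83 or 0.58 at an assumed 15% reducer share with no real effect on reduction, and 0.32 to 1.08 over shares of 10% to 30%. These figures rest on the SAP's 10% and 17% abstinence rates and on assumed reducer shares and mover fractions; they show what is possible, not what is expected. The matter concerns one secondary outcome. The primary outcome is unaffected.

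**What to change.** 1. Replace the Appendix 3 item 7 definition with the main-body one: consumption and CO each reduced by at least 50% from baseline.
2. State the denominator of the reduction outcome in the analysis section.
3. Add a between-arm comparison of abstinent or reduced by at least 50% among all randomised, with missing counted as neither. Show the three categories (abstinent, reduced, neither) by arm, so that the abstinence difference stays visible.
4. Keep the non-abstainer figure for secondary objective 3, labelled as descriptive and not a randomised comparison.
5. Give the outcome a row in Table 5.

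The cost is SAP wording and a small addition to one table, using data already collected. The downside is that the composite is broader than reduction alone, and that the reduction figure for secondary objective 3 becomes descriptive.

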Notes: Since the study protocol was written, a new evaluation of the UK stop smoking services was published [12]. The validated one-year quit rate has declined to 8%. This comprised general practice and pharmacy services with quit rates of 5% and specialist support with quit rates of 10% for individual and 12% for group support. The decline is probably due to a 'hardening' of treatment population, e.g. the services see an increasing number of re-attenders, people with serious health issues etc. Using a quit rate of 10% in the UC arm that provides multi-contact support, and 17% in the EC arm (RR=1.70) the study sample size still provides 86% power to detect such a difference with a two-tail test of proportions.

Assuming the true percentage in both arms is 10%, the 95% confidence interval for the difference in proportions will have width of +/-4% around the observed difference.

If the difference in proportions is non-significant, we will undertake a non-inferiority analysis, using a two-sided confidence interval of the difference in the abstinence percentages between the two arms. Assuming that the true percentages are 10% in the control arm and 12% in the intervention arm, our sample size of 886 will provide 88% power to exclude a difference in favour of the standard group of 4% or more.

Data collection

Baseline

The following variables were collected at baseline:

- **Demographics:** includes age, sex, marital status, ethnicity, employment, level of education, eligibility for free prescriptions,
- **Smoking measures:** Fagerstrom Test for Cigarette Dependence (FTCD) [13], previous stop smoking product use, age first started smoking and whether partner/spouse smokes. Mood and Physical Symptoms Scale (MPSS) [14], carbon monoxide reading
- **Current Health and Medications**
- **Health problems checklist**

The following validated questionnaires are also administered at baseline:

- EQ-5D
- Smoking Cessation and Health Service Use Questionnaire

Follow up

The following variables were collected during follow-up visits:

- Current smoking behaviour
- Mood and Physical Symptoms Scale (MPSS) – 1 and 4 weeks post quit only
- Carbon monoxide reading
- Allocated product use, helpfulness, taste and satisfaction ratings (1 and 4 weeks post quit only), purchase and reasons for stopping (where applicable)
- Non-allocated product use and purchase
- Current health and medications
- Health problems checklist

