***See appendix 3 for how data for each outcome was collected**

Differences in tobacco withdrawal symptoms at 1 and 4 weeks.

Between-group differences in urges to smoke, and changes (from baseline) in tobacco withdrawal symptoms will be examined using ANOVA, in both the whole sample, and abstainers only sample.

Treatment ratings (e.g. satisfaction, taste, helpfulness, reasons for stopping product use)

Differences in mean ratings of treatment effects (product helpfulness, taste, satisfaction and reasons for stopping product use) between groups will be examined using ANOVA (or non-parametric tests where normality cannot be assumed) at 1 and 4 weeks post quit with adjustments where needed for normal distribution. NB. Where 2 NRT products were used and rated, the average rating of the two will be taken.

Adverse reactions (ARs)

The frequency of participants reporting each AR (nausea, sleep disturbance or throat/mouth irritation) at least once will be compared between arms using Chi squared test. The MedDRA coding system will be used.

Changes in respiratory problems

Frequency of respiratory problems at baseline and 12 month follow up will be compared between arms using Chi-squared test.

Cost-efficacy of the interventions.

The economic evaluation is conducted alongside the TEC trial by way of a cost-effectiveness analysis. Following NICE guidance, the analysis will be performed from the National Health Service (NHS) and Personal Social Services (PSS) perspective to reflect NHS England decision-making framework [16]. The analysis from a wider perspective will also be conducted to explore the possible societal impact of the intervention. All costs will be presented in 2015/16 Sterling Pounds (£). The objectives of the analysis are:

1. To assess cost-effectiveness of EC over and above UC at 12-month follow-up (primary outcome);
2. To estimate potential long term cost-effectiveness of the intervention.

These objectives will be achieved by combining data collected within the trial and existing models.

Costs estimation

Intervention cost

The intervention consists of six weekly sessions of standard SSS behavioural support for both arms, a starter kit of e-cigarette for the EC arm and supplies of NRT for the UC arm.

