7-day point prevalence at 52 weeks post TQD, N (%)						

Table 6 – Change in respiratory symptoms

	NRT (N=)		EC (N=)		P-value	Odds Ratio (95% CI)
	Baseline N (%)	12 months N (%)	Baseline N (%)	12 months N (%)		
Shortness of breath						
Wheezing						
Cough						
Phlegm						

Table 7– Percentage participants reporting an adverse reaction at least once

% (N) reporting Adverse Reaction	EC	NRT	P-value
Nausea			
Sleep disturbances			
Throat/mouth irritation			

Table 8 – Differences in urges to smoke at 1 and 4 weeks post quit (abstainers only)

Symptom	1 week post quit		P-value	Mean difference (95% CI)	4 weeks post quit		P-value	Mean difference (95% CI)
	EC	NRT			EC	NRT		
Frequency of urge to smoke – mean (SD)								
Strength of urge to smoke – mean (SD)								
Composite urge score – mean (SD)								

Table 9 – Differences in urges to smoke at 1 and 4 weeks post quit (whole sample)

Symptom	1 week post quit		P-value	Mean difference (95% CI)	4 weeks post quit		P-value	Mean difference (95% CI)
	EC	NRT			EC	NRT		
Frequency of urge to smoke – mean (SD)								
Strength of urge to smoke – mean (SD)								
Composite urge score – mean (SD)								

Table 10 – Change in withdrawal symptoms between baseline and 4-weeks post TQD (abstainers only)

Symptom	NRT (n=)	EC (n=)	P-value	Mean difference, (95% CI)
Depressed – mean (SD)				
Irritable – mean (SD)				
Restless – mean (SD)				
Hungry – mean (SD)				
Poor concentration – mean (SD)				
Composite MPSS score – mean (SD)				

Table 11 – Change in withdrawal symptoms between baseline and 4-weeks post TQD (whole sample)

Symptom	NRT (n=)	EC (n=)	P-value	Mean difference (95% CI)
Depressed – mean (SD)				
Irritable – mean (SD)				
Restless – mean (SD)				
Hungry – mean (SD)				
Poor concentration – mean (SD)				
Composite MPSS score – mean (SD)				

Health economics tables

Table 12: Breakdown of intervention cost (mean [S.D.])

Cost item	NRT (n=xxx)	EC (n=xxx)
Behavioural support sessions		
NRT/EC supplies		
Information sheets		
Total		

Table 13: Unit cost

Services	Unit cost	Sources
Smoking cessation help		
GP		
NHS SSS		
NHS Smoking Helpline service		
Pharmacotherapies		
Patch		
Gum		
Microtab		
Inhaler		
Lozenge		
Spray		
Mouthstrip		
Varenicline		
Bupropion		
Health resources use		
A & E		
Outpatient		
Inpatient		
Day case		
Emergency ambulance		

GP (in office)		
Practice nurse (in office)		
GP (home visit)		
Practice nurse (home visit)		
Prescription		

Table 14: Usage and mean cost of services (mean [S.D.]

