2. A little of the time
3. Some of the time
4. A lot of the time
5. Almost all of the time
6. All of the time

Q7. How strong have these urges been?

1. No urges
2. Slight
3. Moderate
4. Strong
5. Very strong
6. Extremely strong

Definition: Changes in withdrawal symptoms between baseline and 4 weeks on following scale: not at all, slightly, somewhat, very, extremely.

Data source: Q+1 and Q+4 Post Quit CRF,

Q5. For each of the following (depressed, hungry, irritable, poor concentration, restless) rate how you have been feeling over the past week:

1. Not at all
2. Slightly
3. Somewhat
4. Very
5. Extremely

9. Treatment ratings

Definition: Ratings of helpfulness on the following scale: not at all, slightly, somewhat, very, extremely

Data source: Q+1 and Q+4 post quit CRFs

Q8c. Since your last visit/contact how helpful did you find your allocated product(s) in keeping you away from normal cigarettes?

1. Not at all
2. Slightly
3. Somewhat
4. Very
5. Extremely

Definition: Ratings of taste on the following scale: much worse than normal cigarettes, a little worse than normal cigarettes, the same as normal cigarettes, a little better than normal cigarettes, much better than normal cigarettes

Data source: Q+1 and Q+4 post quit CRFs

Q10. How good did it taste?

1. much worse than normal cigarettes
2. a little worse than normal cigarettes
3. the same as normal cigarettes
4. a little better than normal cigarettes
5. much better than normal cigarettes

Definition: Ratings of satisfaction on the following scale: much worse than normal cigarettes, a little worse than normal cigarettes, the same as normal cigarettes, a little better than normal cigarettes, much better than normal cigarettes

Data source: Q+1 and Q+4 post quit CRFs

Q11. How satisfying was it?

1. Much less than normal cigarettes
2. A little less than normal cigarettes
3. The same as normal cigarettes
4. A little more than normal cigarettes
5. Much more than normal cigarettes

10. Adverse reactions (AR) **Definition:** % (N) reporting 'Yes' to adverse reaction on at least one post quit session.

Data source: Health Problems CRF checklist at all post quit sessions (specifically nausea, sleep disturbance and throat/mouth irritation questions).

11. Change in respiratory problems **Definition:** Participants are defined as experiencing the health problem if they responding 'Yes' to it and the given time point.

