Data source: Health Problems CRF checklist (specifically shortness of breath, wheezing, cough and phlegm questions) at baseline and Q+52.

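### Adverse reactions are counted from any post-quit symptom 'Yes' without regard to baseline, so the reported percentages overstate product reaction rates in both arms and may dilute the relative risk

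*SAP*

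**What the plan says.** Secondary objective 6 of the SAP is "Rates of adverse reactions associated with the use of EC compared to standard NRT".

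Appendix 3, outcome 10, makes a participant a case on "reporting 'Yes' to adverse reaction on at least one post quit session". The data source is the "Health Problems CRF checklist at all post quit sessions (specifically nausea, sleep disturbance and throat/mouth irritation questions").

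The section on adverse reactions in the analysis of secondary outcomes takes "The frequency of participants reporting each AR (nausea, sleep disturbance or throat/mouth irritation) at least once" and compares it between arms by chi-squared test, with MedDRA coding. Table 7, titled "Percentage participants reporting an adverse reaction at least once", has one column per arm and a p-value. It has no baseline column and no effect estimate.

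The list of baseline variables under Data collection includes the "Health problems checklist". For the next outcome in Appendix 3, change in respiratory problems, the source is the "Health Problems CRF checklist (specifically shortness of breath, wheezing, cough and phlegm questions) at baseline and Q+52", and Table 6 shows baseline and 12-month counts side by side.

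**The concern.** The objective asks about reactions associated with using a product. A symptom present before randomisation did not begin as a reaction to the allocated product, yet the rule counts it as one if it is reported once afterwards. There are six post-quit contacts (weeks 1, 2, 3, 4, 24 and 52), so a persistent symptom has up to six chances to be counted. MedDRA coding classifies a term and says nothing about when the symptom began.

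Two things are at stake. Readers will take the Table 7 percentages as the reaction rates of e-cigarettes and NRT, and they will be too high for both. Cases carried over from baseline may also hide part of a real difference, and in a harm comparison a pull toward no difference is the unsafe direction.

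**Working it through.** **Check of the formula.** The SAP states no rate, effect or power for adverse reactions. Its only usable power figure is for abstinence: 86% for 10% v 17%. With n per arm, d = p1 − p0 and p̄ the mean of the two rates,

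power = Φ{[d − 1.96·√(2p̄(1−p̄)/n)] / √([p0(1−p0) + p1(1−p1)]/n)}.

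At n = 443 (half of the SAP's 886), 10% v 17% gives 0.863, which matches.

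**Model.** Let b be the baseline prevalence of the symptom, s the chance that a participant with it at baseline answers 'Yes' at least once post-quit, and p the new-onset rate in the others. The SAP rule then counts q = b·s + (1−b)·p. If s is the same in both arms, the risk difference is (1−b)(p1−p0).

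**Inputs.** From the SAP: 443 per arm, two-sided 5%. Assumed: new onset 30% (EC) v 20% (NRT), s = 1 in both arms (full persistence, no product effect in those already affected), and b from 10% to 40%.

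**Worked case, b = 20%.**
- NRT: 0.20 + 0.80 × 0.20 = 36%. EC: 0.20 + 0.80 × 0.30 = 44%. RR = 0.44/0.36 = 1.22; risk difference 8 points instead of 10.
- Power, SAP rule: (0.08 − 1.96 × 0.0329)/0.0328 = 0.47, so 68%.
- New onset only, n = 443 × 0.80 ≈ 354 per arm: RR 1.50; (0.10 − 1.96 × 0.0325)/0.0323 = 1.12, so 87%.
- Share of counted cases already present at baseline: 0.20/0.36 = 56% (NRT) and 0.20/0.44 = 45% (EC).

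| b | SAP rule, NRT v EC | RR | Power, SAP rule | Power, new onset (RR 1.50) |
|---|---|---|---|---|
| 10% | 28% v 37% | 1.32 | 82% | 91% |
| 20% | 36% v 44% | 1.22 | 68% | 87% |
| 40% | 52% v 58% | 1.12 | 43% | 76% |

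**Varying the assumptions at b = 20%.**
- Persistence s = 0.8: RR 1.25, power 70%. Persistence s = 0.5: RR 1.31, power 74%.
- Rarer events, new onset 17% v 10%, s = 1: 33.6% v 28.0%, RR 1.20, power 44%, against RR 1.70 and 78% for new onset.
- Product effect in those already affected, s = 70% (EC) v 60% (NRT), new onset 30% v 20%: 0.20 × 0.60 + 0.80 × 0.20 = 28% and 0.20 × 0.70 + 0.80 × 0.30 = 38%. The SAP rule now has 89% power, slightly above the 87% for new onset only. At b = 40% the figures are 86% and 76%.

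**Comparing all participants, stratified by the baseline answer (b = 20%).**
- With s = 1, everyone in the baseline-positive stratum is a case, so that stratum adds nothing to the numerator or the variance of the stratified test. Power equals the new-onset 87%. The pooled RR stays 1.22, because it averages over both strata.
- With 70% v 60%, the difference is 0.10 in both strata. Null variance: (0.8 × 0.25 × 0.75 + 0.2 × 0.65 × 0.35) × 2/443 = 0.000883. Alternative variance: (0.8 × 0.37 + 0.2 × 0.45)/443 = 0.000871. Then (0.10 − 1.96 × 0.0297)/0.0295 = 1.42, so about 92%.

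In both cases at b = 20%, the stratified comparison does at least as well as either alternative.

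**The case against.** The case against has real force.

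- **The form is not shown.** The checklist is listed at baseline, but only the respiratory items are expressly named there. That nausea, sleep disturbance and throat/mouth irritation were also asked at baseline is inferred from the shared checklist name. The post-quit question might itself ask about new or product-related symptoms. This stands and limits confidence.
- **The comparison is not invalid.** A reader might infer that the rule biases one arm against the other. It does not: randomisation balances baseline symptoms in expectation, and the chi-squared test is fair for what it counts.
- **Power is not always lost.** A reader might infer that the rule necessarily weakens the search for harm. The 70% v 60% scenario shows otherwise. A product that keeps a sore throat going does harm, and an analysis restricted to participants free of the symptom at baseline would discard that evidence. So replacing the main comparison by new onset alone is not warranted.
- **Table 6 is not a contradiction.** The respiratory outcome is defined as a change and needs a baseline; an 'at least once' count does not. The contrast shows only that the SAP makes use of baseline answers from this checklist.
- **New onset is not relatedness.** Baseline is at week −1, before the quit date, and stopping smoking can itself bring new symptoms. A causality rule may also sit in the protocol, so its absence here is not a finding.

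What survives is that the three places in the SAP that fix this outcome make no use of the baseline answer, while the label and the objective both speak of reactions.

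**Conclusion.** The point holds in a limited form. Followed as written, the SAP reports symptoms present before randomisation as adverse reactions, so the absolute percentages overstate reaction rates in both arms whenever baseline prevalence and persistence are above zero. In the illustration at 20% prevalence, about half of the counted cases predate randomisation.

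The effect on the comparison is conditional. With little product effect in those already affected, the relative risk moves toward 1 (1.50 to 1.22 in the worked case) and power drops (87% to 68%). With a product effect in that group as well, the power loss can disappear. The rates, prevalences and persistence are all assumptions, because the SAP gives none.

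The documents do not support a claim of a false difference between arms or of a certain loss of power. The primary outcome is untouched. Confidence is moderate, since the CRF is not shown. The change is worth making because it is nearly free.

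**What to change.** First confirm on the CRF that the three items are asked at baseline. If they are, change Appendix 3 outcome 10, the adverse reactions paragraph and Table 7 together:

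1. Add baseline N (%) columns by arm to Table 7, as in Table 6.
2. Keep all participants, and compare arms with a risk ratio and 95% CI stratified by, or adjusted for, the baseline answer to the same item. The SAP's general analysis principles already call for an effect estimate with a 95% CI for every outcome; Table 7 has only a p-value.
3. Add a row for new-onset symptoms among participants who answered 'No' at baseline. This row gives the undiluted relative risk.
4. Label the any-'Yes' row as a symptom reported post-quit, not as an adverse reaction.

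The cost is one derived variable and a slightly longer table, with no new data collection. Neither row captures worsening of an existing symptom or establishes that the product caused it, and a footnote to the table should say so. If the items turn out not to be on the baseline form, only the relabelling and the risk ratio with its interval (without baseline adjustment) remain possible.
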